3.1.1 Administrative structure of the trial

The trial will be performed by investigators and study nurses experienced in phase I trials and in conducting drug-drug interaction trials. Safety laboratory tests will be performed at the investigator site. Pharmacokinetic evaluations will be performed by Boehringer Ingelheim.

On-site monitoring will be performed by a CRO appointed by Boehringer Ingelheim.

All trial relevant documentation will be stored at a CRO and will be harmonised with Boehringer Ingelheim's CTMF at the end of the trial. Trial relevant documentation which must remain at the trial site will be filed in the investigator site file (ISF) at the investigator site.

The principal investigator who will sign the clinical trial report of this trial has been appointed by Boehringer Ingelheim. The principal investigator has experience in these types of trials and investigations.

3.2 DISCUSSION OF TRIAL DESIGN, INCLUDING THE CHOICE OF CONTROL GROUP(S)

The primary objective of this study is to determine the influence of co-administration of volasertib with itraconazole on the pharmacokinetics of volasertib in comparison to volasertib alone in cancer patients. No control group will be recruited.

The intra-individual comparison is preferred as each of the subjects will serve as his own control and the precision is therefore expected to be higher than with a group comparison.

The fixed sequence is considered appropriate for an unbiased investigation of the volasertib PK due to the negligible carry-over effect from the first treatment cycle and because unspecific time effects on the volasertib PK are not to be expected.

3.3 SELECTION OF TRIAL POPULATION

It is planned that 24 patients, at least 8 male and 8 female, will be recruited for this study (see [Section 7.6](#)). Patients not completing treatment cycle 2 will be replaced (see [Section 3.3.4.1](#)).

24 patients will be recruited for this study in order to have at least data for 24 patients completing the first treatment cycle with co-administration of itraconazole and volasertib and the second cycle with volasertib. The recruitment period is expected to last approximately 12 months.

A log of all patients included into the study (i.e. having given informed consent) will be maintained in the ISF at the investigational site irrespective of whether they have been treated with investigational drug or not.

Proprietary confidential information.

© 2017 Boehringer Ingelheim International GmbH or one or more of its affiliated companies. All rights reserved.
This document may not - in full or in part - be passed on, reproduced, published or otherwise used without prior written permission.

3.3.1 Main diagnosis for study entry

Adult male and female patients with histo- or cytologically confirmed diagnosis of advanced / metastatic solid tumour.

3.3.2 Inclusion criteria

Patients must meet all of the following inclusion criteria to be eligible for entry into the trial:

1. Patients with histologically or cytologically confirmed diagnosis of advanced, non resectable and / or metastatic solid tumour, for whom conventional treatment has failed, or for whom no therapy of proven efficacy exists, or who are not amenable to established forms of treatment based on the investigator's assessment
2. Male or female
3. Age ≥ 18 and ≤ 70 years
4. Written informed consent consistent with ICH-GCP and local legislation
5. Eastern Cooperative Oncology Group (ECOG) performance score ≤ 2
6. Recovery from CTCAE Grade ≥ 2 therapy-related toxicities from previous chemo-, hormone-, immuno-, or radiotherapy (except alopecia)

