3.3.3 Exclusion criteria

Patients presenting with any of the following will not be included in the trial:

1. Serious concomitant non-oncological disease considered by the investigator to be incompatible with the protocol
2. Active infectious disease
3. Viral hepatitis, HIV infection
4. Clinical evidence of active brain metastasis or leptomeningeal disease during the past 6 months
5. Second malignancy currently requiring active therapy (except for hormonal / antihormonal treatment e.g. in prostate or breast cancer)
6. Absolute neutrophil count less than $1,500/\text{mm}^3$
7. Platelet count less than $100,000/\text{mm}^3$
8. Total bilirubin greater than $1.5 \text{ mg/dL} (> 26 \mu\text{mol/L, SI unit equivalent})$
9. Aspartate amino transferase (AST) and / or alanine amino transferase (ALT) greater than 2.5 times the upper limit of normal (if related to liver metastases greater than five times the upper limit of normal)
10. Serum creatinine greater than $2 \times \text{ULN}$.
11. QTcF prolongation $> 470 \text{ ms}$ or QT prolongation deemed clinically relevant by the investigator (e.g., congenital long QT syndrome). The QTcF will be calculated as the mean of the 3 ECGs taken at screening

Proprietary confidential information.

© 2017 Boehringer Ingelheim International GmbH or one or more of its affiliated companies. All rights reserved.
This document may not - in full or in part - be passed on, reproduced, published or otherwise used without prior written permission.

12. Male patients who are sexually active and having a partner with childbearing potential and unwilling to use a medically acceptable method of contraception during the trial and for at least six months after end of active therapy
13. Female patients with childbearing potential and unwilling to use a medically acceptable method of contraception during the trial and for at least six months after end of active therapy. Woman of childbearing potential (premenopausal female) is defined as the female who is not surgically sterilised by hysterectomy or bilateral tubal ligation or post-menopausal for at least 12 months.
14. Treatment with other investigational drugs or participation in another clinical trial within the past four weeks prior to start of therapy or concomitantly with this trial

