15. Chemo-, radio- immuno-, or molecular-targeted cancer-therapy within the past four weeks prior to start of therapy or concomitantly with this trial. This restriction does not apply to steroids, bisphosphonates hormonal / antihormonal treatment (e.g. in prostate or breast cancer).
16. Patients unable to comply with the protocol
17. Alcohol abuse more than an average 3 units of alcoholic beverages per day or more than 21 units per week (1 unit equals 0.5 pint [285 mL] of beer or lager, 1 glass [125 mL] of wine, 25 mL shot of 40% spirit)) or drug abuse
18. Life expectancy less than 12 weeks
19. Potent CYP 3A4 and P-glycoprotein inhibitors other than the study drug or inducers between one week prior to first drug administration or expected treatment with a respective drug until the last PK sample is collected
 - a) Strong CYP 3A4 inhibitors: atazanavir, clarithromycin, indinavir, itraconazole (other than study drug), ketoconazole, nefazodone, nelfinavir, ritonavir, saquinavir, telithromycin
 - b) CYP 3A4 inducers: carbamazepine, rifampicin
 - c) P-gp inhibitors: cyclosporine, erythromycin, itraconazole (other than study drug), ketoconazole, quinidine, phenobarbital salt with quinidine, ritonavir, valspar, verapamil
 - d) P-gp inducers: hypericum perforatum, rifampicin
20. History of allergy/hypersensitivity (including allergy to study drug or its excipients) based on the investigator's assessment
21. Excessive physical activities (within one week prior to administration and until the last PK sample is taken)

Exclusion criteria specific for this study:

22. Veins unsuitable for blood sampling and infusion

For study restrictions refer section [4.2.2](#).

Proprietary confidential information.

© 2017 Boehringer Ingelheim International GmbH or one or more of its affiliated companies. All rights reserved.
This document may not - in full or in part - be passed on, reproduced, published or otherwise used without prior written permission.

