4.2.2 Restrictions

4.2.2.1 Restrictions regarding concomitant treatment

Additional chemo-, immuno-, hormone, radio-, or molecular-targeted cancer-therapy is not permitted during the study. These restrictions do not apply to steroids and bisphosphonates as well as to hormonal / antihormonal treatment e.g. in prostate or breast cancer. For symptom control, palliative radiotherapy may be permitted after discussion with the BI Clinical Monitor.

The following potent CYP 3A4 and P-glycoprotein inhibitors or inducers are not permitted from one week prior to first drug administration until the last PK sample is collected:

Strong CYP 3A4 inhibitors: atazanavir, clarithromycin, indinavir, ketoconazole, itraconazole, nefazodone, neflavinavir, ritonavir, saquinavir, telithromycin

CYP 3A4 inducers: carbamazepine, rifampicin

P-gp inhibitors: cyclosporine, erythromycin, ketoconazole, itraconazole, quinidine, phenobarbital salt with quinidine, ritonavir, valspodar, verapamil

P-gp inducers: hypericum perforatum (St. John's wort), rifampicin

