5.3.2.2 Demographics and history

Demographics (sex, birth date, race), information on smoking and alcohol status, and baseline conditions will be collected during the screening.

History of tumour will also be obtained. The type of tumour, the date of first histological diagnosis (month and year may be sufficient), and the primary tumour site will be reported into the eCRF. The differentiation grade (not specified, poorly differentiated, moderately differentiated, well differentiated), the number and location of metastatic sites as well as the stage according to the tumour, (lymph) node, metastasis (TNM) classification and the [REDACTED]

[REDACTED] / American Joint Committee on Cancers (AJCC) classification will be provided as obtained at diagnosis. It will also be recorded whether visceral involvement, bone involvement or soft tissue involvement is present (yes, no, unknown). Previous surgery will be reported. Previously administered radio-, chemo-, immuno-, molecular-targeted, and hormone therapy will be reported including start and end dates (month and year may be sufficient), the therapy protocol with the number of cycles (chemo-, immunotherapy), the best response obtained (complete response, partial response, stable disease, progressive disease, unknown) as well as whether the therapy was given as neoadjuvant, adjuvant, or palliative therapy. Concerning previous radiotherapy the total radiation dose and radiation field will be recorded.

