6.2 IMPORTANT PROTOCOL VIOLATIONS

[Table 6.2: 1](#) contains the categories in which important PVs are classified. Categories for manually assessed important PVs, i.e. important PVs that are detected manually at the sites and cannot be detected through the database, are not shown in this table but will be finalised before DBL and documented in the final BRPM minutes.

Consistency checks will be prepared for identifying violations of time windows.

Table 6.2: 1 Important protocol violations

Category/ Code		Description	Example/Comment
A		Entrance criteria not met	
	A1	Inclusion criteria not met	Inclusion criteria 6 not met as specified in the protocol as this is safety related; see SOP) Other inclusion criteria violation will be manually reviewed.
	A2	Exclusion criteria not met	Laboratory criteria 6-11, 19. Violations on other exclusion criteria will be manually reviewed.
B		Informed consent	
	B1	Informed consent not available/not done	Informed consent date missing
	B2	Informed consent too late	Informed consent date <actual consent date> was after Visit 1 date <Visit 2 date>
C		Trial medication and randomization	

Table 6.2: 1 (continued) Important protocol violations

Category/ Code	Description	Example/Comment
C1.1	Non-compliance	Missing itraconazole doses during either pre-volasertib administration period or on the day of volasertib administration is considered IPV..
C1.2	Non-compliance	Missing itraconazole doses in the post-volasertib administration period will be documented and reviewed case by case
C2.1	Volasertib infusion late	Volasertib infusion not immediately after medicine preparation will be documented and reviewed case by case
D	Concomitant medication	
D2	Prohibited medication use	
 • Strong inhibitors of CYP3A4 • Inducers of CYP3A4 • Inhibitors of P-gp • Inducers of P-gp (CTP 4.2.2.1)
E	Missing data (for primary endpoints)¹	
E4	Certain violations of procedures used to measure primary and secondary data	Un-evaluable PK results for reasons other than study discontinuation.
F	Incorrect timing (for primary and secondary endpoints)²	
F5	Certain violations of the time schedule used to measure primary and secondary data	

KEY: Hb = haemoglobin, Hct = Haematocrit, Tx = transfusion, PPS – Per Protocol Set

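### Inclusion criterion 6 omits molecular-targeted therapy from the toxicity-recovery requirement, although the protocol treats it as a separate treatment class elsewhere

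*Protocol*

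**What the plan says.** Criterion 6 in protocol section 3.3.2 asks for "Recovery from CTCAE Grade ≥ 2 therapy-related toxicities from previous chemo-, hormone-, immuno-, or radiotherapy (except alopecia"). That is four classes: chemo-, hormone-, immuno- and radiotherapy.

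Three other places in the protocol name molecular-targeted therapy separately:

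- Exclusion 15 (section 3.3.3) bars "Chemo-, radio- immuno-, or molecular-targeted cancer-therapy within the past four weeks prior to start of therapy or concomitantly with this trial". This rule is about elapsed time and does not mention recovery.
- Section 4.2.2.1 states that "Additional chemo-, immuno-, hormone, radio-, or molecular-targeted cancer-therapy is not permitted during the study".
- Section 5.3.2.2 states that "Previously administered radio-, chemo-, immuno-, molecular-targeted, and hormone therapy will be reported including start and end dates".

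SAP Table 6.2:1, row A1, gives as its example of an important violation "Inclusion criteria 6 not met as specified in the protocol as this is safety related"; violations of other inclusion criteria go to manual review. Both pharmacokinetic analysis sets in SAP section 6.3 require the absence of important protocol violations.

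**The concern.** The protocol expects patients who have already received targeted drugs, because it collects that history by class and date. For the other four classes it insists that Grade 2 or higher toxicity has resolved before entry. For targeted therapy it asks only for a four-week gap.

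The stakes lie in the DRT count. Protocol section 5.2.2.1 counts an exacerbation of a pre-existing condition as an adverse event. Under section 5.2.6, a drug-related non-haematological event of Grade 3 or higher is in general a DRT. A patient who enters with Grade 2 toxicity from an earlier targeted drug is thus one grade away from a possible DRT. Section 4.1.3.1 lowers the volasertib dose for subsequent patients if more than 1 of 6 has a DRT in cycle 1, and section 5.2.6 defines the MTD by the same count. With so few patients behind the rule, a single misattributed event carries weight.

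**Working it through.** **Step 1: compare the lists.**

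| Place in protocol | Chemo | Hormone | Immuno | Radio | Molecular-targeted |
|---|---|---|---|---|---|
| 3.3.2, criterion 6 (recovery) | yes | yes | yes | yes | **no** |
| 3.3.3, exclusion 15 (four-week gap) | yes | exempt | yes | yes | yes |
| 4.2.2.1 (concomitant treatment) | yes | yes, with exemption | yes | yes | yes |
| 5.3.2.2 (history) | yes | yes | yes | yes | yes |

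Sections 4.2.2.1 and 5.3.2.2 list five classes. Criterion 6 lists four of the same five. Targeted therapy cannot be read into chemo- or immunotherapy without making the other lists redundant.

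**Step 2: look for another rule that closes the gap.**

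- Exclusion 15 sets an interval, not recovery.
- Exclusion 1 covers "Serious concomitant non-oncological disease considered by the investigator to be incompatible with the protocol". It is discretionary and carries no grade or recovery requirement.
- Exclusion 2 (active infection) and the ECOG limit apply whatever the cause, but do not require recovery from toxicity.
- Exclusions 6 to 11 (neutrophils, platelets, bilirubin, AST/ALT, creatinine, QTcF) also apply whatever the cause, but only to those measurements.

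What remains is non-laboratory, non-QT toxicity of Grade 2 or higher from a targeted drug stopped more than four weeks earlier. No explicit rule requires it to have resolved. Because such a patient fails no inclusion criterion, SAP row A1 has nothing to flag, either automatically or on manual review.

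**Step 3: size of the effect on the dose rule.** The documents give neither a DRT rate nor the frequency of carried-in toxicity, so the following inputs are assumptions: independent patients, a DRT risk of 10% for an unaffected patient, and a risk q for one affected patient among six.

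All six at 10%:

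P(at least 2) = 1 − 0.9⁶ − 6 × 0.1 × 0.9⁵ = 1 − 0.5314 − 0.3543 = 0.114.

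One patient at q, five at 10%:

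- P(0) = (1 − q) × 0.9⁵ = (1 − q) × 0.59049
- P(1) = q × 0.59049 + (1 − q) × 5 × 0.1 × 0.9⁴ = q × 0.59049 + (1 − q) × 0.32805
- P(at least 2) = 1 − 0.59049 − (1 − q) × 0.32805 = 0.0815 + 0.32805 × q

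| Risk q in the one affected patient | P(more than 1 DRT in 6) |
|---|---|
| 10% (no effect) | 11.4% |
| 20% | 14.7% |
| 40% | 21.3% |

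If two of six patients were at 20% and four at 10%:

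- P(0) = 0.8² × 0.9⁴ = 0.4199
- P(1) = 2 × 0.2 × 0.8 × 0.9⁴ + 0.8² × 4 × 0.1 × 0.9³ = 0.2100 + 0.1866 = 0.3966
- P(at least 2) = 1 − 0.4199 − 0.3966 = 18.4%

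**The case against.** The best defence is that this is loose wording rather than a deliberate gap. Protocol section 2.3, describing the non-interaction part, names only cytotoxic and immunological anticancer treatments, so criterion 6 is not the only list that leaves out targeted therapy. Its authors may have meant prior anticancer treatment in general. That may be so, but section 2.3 is a summary, whereas criterion 6 is an entry rule that sites and the SAP apply as written.

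The DRT route also has safeguards. An event counts only if judged drug related; section 5.2.2.1 tells the investigator to weigh confounding factors and relevant history; and prior targeted therapy and baseline conditions are recorded. Exclusions 6 and 7 set entry limits for the cell counts behind the haematological DRTs. This stands, and it confines the exposure to the non-haematological part of the definition.

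A reader might infer more than the documents support:

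- *That such a patient is simply eligible.* The patient is not excluded by criterion 6; the other limits and the investigator's judgement still apply.
- *That the risk of triggering de-escalation doubles or triples.* Raising all six patients from 10% to 15% or 20% gives 22% or 34%, but this supposes that the average risk of the whole group rises. With one affected patient in six, an average of 15% needs that patient at 40% ((5 × 10 + 40) / 6 = 15), and an average of 20% needs 70% ((5 × 10 + 70) / 6 = 20).
- *That carried-in toxicity explains the move to 250 mg after the first three patients, recorded in SAP section 4.* Nothing in the documents says so.
- *That the primary result is affected.* It is a within-patient pharmacokinetic ratio with no confirmatory test, and no effect on it is shown. The safety comparison of cycles 1 and 2 is descriptive.

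Finally, the SAP describes treatment in the past tense, and protocol version 4.0 simplifies procedures because the programme was discontinued. A changed entry criterion may reach few or no patients.

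**Conclusion.** The omission is real and is visible by comparing the protocol's own lists. Its scope is narrow: non-laboratory, non-QT toxicity of Grade 2 or higher from a targeted drug stopped more than four weeks earlier, in a patient whom the investigator does not exclude under exclusion 1. The consequence is a gap in an entry rule that the SAP itself treats as safety related, and a possible contribution to the small DRT count behind the dose rule.

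The size is unknown. Under the assumed 10% background, doubling the risk in one of six patients raises the chance of more than one DRT from about 11% to 15%; that figure depends on the assumed rates and on independence between patients. The point does not bear on the sample size or on the primary pharmacokinetic estimate. It is worth correcting because it concerns patient safety at entry and costs almost nothing.

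**What to change.** Add molecular-targeted therapy to inclusion criterion 6, so that it names the same five classes as sections 4.2.2.1 and 5.3.2.2. SAP Table 6.2:1, row A1, refers to criterion 6 and would then cover it without a change of its own. The addition would not make criterion 6 identical to exclusion 15, which exempts hormonal treatment; that difference can stay, because one rule concerns recovery and the other time since treatment.

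If enrolment is already closed, use data that the protocol collects: compare recorded prior targeted therapy and baseline conditions with the cycle 1 DRTs, and report any overlap in the trial report.

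The cost is one added term. The downside is that an occasional patient waits for recovery or is not enrolled. The retrospective check needs no new data collection.

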3.3.3 Exclusion criteria

Patients presenting with any of the following will not be included in the trial:

1. Serious concomitant non-oncological disease considered by the investigator to be incompatible with the protocol
2. Active infectious disease
3. Viral hepatitis, HIV infection
4. Clinical evidence of active brain metastasis or leptomeningeal disease during the past 6 months
5. Second malignancy currently requiring active therapy (except for hormonal / antihormonal treatment e.g. in prostate or breast cancer)
6. Absolute neutrophil count less than $1,500/\text{mm}^3$
7. Platelet count less than $100,000/\text{mm}^3$
8. Total bilirubin greater than $1.5 \text{ mg/dL} (> 26 \mu\text{mol/L, SI unit equivalent})$
9. Aspartate amino transferase (AST) and / or alanine amino transferase (ALT) greater than 2.5 times the upper limit of normal (if related to liver metastases greater than five times the upper limit of normal)
10. Serum creatinine greater than $2 \times \text{ULN}$.
11. QTcF prolongation $> 470 \text{ ms}$ or QT prolongation deemed clinically relevant by the investigator (e.g., congenital long QT syndrome). The QTcF will be calculated as the mean of the 3 ECGs taken at screening

Proprietary confidential information.

© 2017 Boehringer Ingelheim International GmbH or one or more of its affiliated companies. All rights reserved.
This document may not - in full or in part - be passed on, reproduced, published or otherwise used without prior written permission.

12. Male patients who are sexually active and having a partner with childbearing potential and unwilling to use a medically acceptable method of contraception during the trial and for at least six months after end of active therapy
13. Female patients with childbearing potential and unwilling to use a medically acceptable method of contraception during the trial and for at least six months after end of active therapy. Woman of childbearing potential (premenopausal female) is defined as the female who is not surgically sterilised by hysterectomy or bilateral tubal ligation or post-menopausal for at least 12 months.
14. Treatment with other investigational drugs or participation in another clinical trial within the past four weeks prior to start of therapy or concomitantly with this trial
15. Chemo-, radio- immuno-, or molecular-targeted cancer-therapy within the past four weeks prior to start of therapy or concomitantly with this trial. This restriction does not apply to steroids, bisphosphonates hormonal / antihormonal treatment (e.g. in prostate or breast cancer).
16. Patients unable to comply with the protocol
17. Alcohol abuse more than an average 3 units of alcoholic beverages per day or more than 21 units per week (1 unit equals 0.5 pint [285 mL] of beer or lager, 1 glass [125 mL] of wine, 25 mL shot of 40% spirit)) or drug abuse
18. Life expectancy less than 12 weeks
19. Potent CYP 3A4 and P-glycoprotein inhibitors other than the study drug or inducers between one week prior to first drug administration or expected treatment with a respective drug until the last PK sample is collected
 - a) Strong CYP 3A4 inhibitors: atazanavir, clarithromycin, indinavir, itraconazole (other than study drug), ketoconazole, nefazodone, nelfinavir, ritonavir, saquinavir, telithromycin
 - b) CYP 3A4 inducers: carbamazepine, rifampicin
 - c) P-gp inhibitors: cyclosporine, erythromycin, itraconazole (other than study drug), ketoconazole, quinidine, phenobarbital salt with quinidine, ritonavir, valspar, verapamil
 - d) P-gp inducers: hypericum perforatum, rifampicin
20. History of allergy/hypersensitivity (including allergy to study drug or its excipients) based on the investigator's assessment
21. Excessive physical activities (within one week prior to administration and until the last PK sample is taken)

Exclusion criteria specific for this study:

22. Veins unsuitable for blood sampling and infusion

For study restrictions refer section [4.2.2](#).

Proprietary confidential information.

© 2017 Boehringer Ingelheim International GmbH or one or more of its affiliated companies. All rights reserved.
This document may not - in full or in part - be passed on, reproduced, published or otherwise used without prior written permission.

